2.2.1 Subgroup of interest

Not applicable.

2.3 Participant disposition, demographics and other baseline characteristics

The FAS will be used for the analyses below. Participant disposition, demographics and other baseline characteristics will be summarized by dose cohort (Adults with sabatolimab 400 mg, Adults with sabatolimab 800 mg, Adults with azacitidine and sabatolimab combination, Adolescents with sabatolimab monotherapy).

2.3.1 Participant disposition

Number (%) of participants screened and enrolled will be summarized by country and center.

The number (%) of participants in the FAS who started treatment, are still on treatment, who entered and discontinued post-treatment follow-up will be summarized together with the respective reasons for treatment/post-treatment follow-up discontinuation. All disposition information will be listed.

The number (%) of participants in the FAS with any protocol deviation will be tabulated by deviation category and will be listed.

2.3.2 Demographic and other baseline/disease characteristics

Demographic and other baseline data including disease characteristics will be listed and summarized descriptively for all participants from the FAS.

BMI (kg/m^2) at baseline will be calculated as weight[kg] / (height[m]²) using weight at baseline and height at screening. Body Surface Area (BSA) is based on the Mosteller formula described in Section 2.4.1.

Details on AML diagnosis (initial diagnosis, ELN classification, current disease status (de novo or secondary) and cytogenetic abnormalities will be tabulated and time since diagnosis summarized.

Details on allogeneic transplant history (disease remission status at time of transplant, transplantation timing, etc. as well as history of acute Graft-versus-Host Disease (GvHD) and chronic GvHD) will be tabulated and time since transplant summarized.

Relevant medical histories and current medical conditions at baseline will be summarized by system organ class and preferred term. Medical history and current medical conditions will be

Novartis	Confidential	Page 19 of 35
SAP – Amendment 1		CMBG453F12201

coded using the Medical Dictionary for Regulatory Activities (MedDRA) terminology. The MedDRA version used for reporting will be specified in the CSR and as a footnote in the applicable outputs.

2.4 Treatments (study treatment, rescue medication, concomitant therapies, compliance)

The Safety set will be used for the analyses below and summary tables will be presented by dose cohort (Adults with sabatolimab 400 mg, Adults with sabatolimab 800 mg, Adults with azacitidine & sabatolimab combination, Adolescents with sabatolimab monotherapy).

2.4.1 Study treatment / compliance

The duration of exposure to sabatolimab, azacitidine, and to the combination sabatolimab+azacitidine for the combination cohort only, as well as the actual dose intensity, relative dose intensity, dose changes, will be summarized by descriptive statistics.

Duration of exposure

The duration of exposure (in months) will be summarized for study treatment (combination) and for each study drug individually (sabatolimab and azacitidine) based on summary statistics and categorical analyses (e.g. exposure < 1 month, at least 1 month, at least 2 months etc.). Details on start and end dates used for derivations are outlined in Appendix Section 5.1.

Cumulative dose

For sabatolimab the actual cumulative dose in mg is the sum of "dose administered" from the eCRF of all cycles during the exposure to sabatolimab.

For azacitidine, the actual dose in mg/m^2 in each cycle is the "dose administered" in mg during that cycle divided by the body surface area (BSA) at the beginning of the cycle using the weight measured before the infusion at that cycle. If the weight is not collected at the beginning of the cycle, the weight from the previous visit will be considered. The actual cumulative dose in mg/m^2 is then the sum of all cycles. The following formula is used for BSA:

BSA (m²) = $\sqrt{\text{Weight (kg) * Height at screening (cm)/3600}}$ (Mosteller formula)

Dose intensity and relative dose intensity

Dose intensity is defined for participants with non-zero duration of exposure. For participants who did not take the drug, the dose intensity is by definition equal to zero. The actual dose intensity (computed as the ratio of actual cumulative dose received and duration in days from first to last cycle initiated) and the relative dose intensity (computed as the ratio of actual dose intensity and planned dose intensity) will be summarized for each study treatment component by descriptive statistics. The planned dose intensity for each of the study drugs is the ratio of planned cumulative dose and duration in days from first to last cycle initiated:

- For sabatolimab the planned dose intensity is 400 mg/28 days or 800 mg/28 days,
- For azacitidine, the planned dose intensity is 50 mg/m²/day which is equivalent to 250 mg/m²/28 days,

Novartis	Confidential	Page 20 of 35
SAP – Amendment 1		CMBG453F12201

The relative dose intensity is then computed as the ratio of actual dose intensity and planned dose intensity. As example, if a participant received sabatolimab at 600 mg Q4W on average throughout the study (instead of the 800 mg Q4W as planned per protocol), the relative dose intensity for this participant is 0.75.

Details on the duration in days from the first to last cycle initiated for the derivation of the dose intensity and the relative dose intensity are provided in Appendix Section 5.1.

Dose reduction, dose interruption and permanent discontinuations

The number (%) of participants with any dose changes (incl. reductions, interruptions, or permanent discontinuations) and the reasons (e.g. AE, dosing error, dispensing error) will be taken from the 'Study Treatment eCRF' and summarized by study drug. The total duration of interruptions by participant will be summarized for the study population by time intervals, e.g. < 1week, $\geq 1-< 2$ weeks, $\geq 2-< 3$ week etc. (these time intervals may be adjusted depending on the observed data).

2.4.2 Prior, concomitant and post therapies

Concomitant medications and significant non-drug therapies prior to and after the start of the study treatment will be summarized according to the Anatomical Therapeutic Chemical (ATC) classification system.

Prior anti-neoplastic medications will be summarized using the FAS. Medications will be summarized by ATC class and preferred term. Prior surgical and medical procedures will be summarized by SOC and PT.

Anti-neoplastic medications and cellular therapies after discontinuation of study treatment during follow-up within the study will be summarized by ATC class and preferred term. Donor lymphocyte infusions (DLI) will be listed.

2.5 Analysis of the primary objective

For adults, the primary safety objective is to determine whether sabatolimab given in monotherapy at the tested dose level (400 mg and 800 mg) leads to an unacceptable level of toxicity including treatment emergent aGvHD and cGvHD and to determine the dose recommended for expansion (RDE).

For adolescents, the primary objective is to determine whether sabatolimab given in monotherapy at the recommended dose for adults does not lead to an unacceptable level of toxicity in adolescents. Following Novartis decision to permanently hold recruitment for non-safety related reasons, only one adolescent was enrolled in part 2. Thus, all analyses on the adolescent cohort could not be perform and only listings will be provided.

The primary efficacy objective is to assess the proportion of adult participants with AML and MRD+ post-aHSCT (according to local assessment) who remain with no evidence of hematologic relapse after 6 cycles of study treatment for each cohort (sabatolimab at the RDE in monotherapy and sabatolimab at the RDE in combination with azacitidine).

2.5.1 **Primary endpoints**

Primary safety analysis in adults (safety run-in part only)

The primary endpoint is the incidence of DLTs between Cycle 1 Day 1 and the end of Cycle 2 of treatment in participants enrolled in the safety run-in part and included in the DDS.

Details on the definition of DLT which are to be captured in the Adverse Event eCRF are defined in Table 6-2 in the protocol.

Primary safety analysis in adolescent (Cohort 5 only) - Not assessable

The primary endpoint is the incidence of DLTs between Cycle 1 Day 1 and the end of Cycle 2 of treatment in participants enrolled in the adolescent cohort (Cohort 5) and included in the DDS.

The same definition of DLT is applied for adolescents and adults.

Primary efficacy analysis in adults (safety run-in and expansion parts)

The primary endpoint is the proportion of participants included in the FAS with no evidence of hematologic relapse after 6 cycles of study treatment or discontinue earlier for adults treated with sabatolimab at the recommended dose for expansion (RDE) in monotherapy and separately for adults treated with sabatolimab in combination with azacitidine.

Details on the definition of response categories which are to be captured in the eCRF by the investigator are defined in Table 8-3 of the protocol.

2.5.2 Statistical hypothesis, model, and method of analysis

Primary safety analysis in adults (safety run-in part only)

A Bayesian model will be used to assess whether sabatolimab at the two tested dose levels is not meeting an unacceptable level of toxicity in adults from the DDS. The threshold to qualify for an acceptable level of toxicity was higher (50%) than the standard threshold used in phase I study (33%) because:

- aGvHD and cGvHD are included in the DLT definition,
- Yet, the curative efficacy of aHSCT is attributable to GvL, which inherently maybe associated with risk of GvHD,
- Therefore, post-aHSCT immunomodulatory interventions, including sabatolimab, that promote GvL could potentially induce GvHD and other immune-related adverse events.

The relationship between the dose of sabatolimab and the probability of DLT is modeled using a logistic regression detailed in Appendix Section 16.6 of the protocol. A summary of the characteristics of this Bayesian model is presented below:

- A single agent dose-DLT logistic model will assess the toxicity risk of sabatolimab.
- Taking into account the lack of historical data and the intrinsic risk of GvHD (which is part of the DLT definition) in the post-aHSCT setting, a weakly informative priors with means corresponding to a risk of DLT at the reference dose of 15%, and a doubling in dose leading to a doubling in the odds of the risk of a DLT were selected.

Novartis	Confidential	Page 22 of 35
SAP – Amendment 1		CMBG453F12201

• The prior risk of excessive toxicity (i.e. risk of DLT within [50%-100%]) is 10.3% for the sabatolimab 400 mg Q4W and 19.4% for the sabatolimab 800 mg Q4W.

After each cohort in the safety run-in part, the posterior distribution for the risk of DLT for new participants at the dose level of interest will be evaluated. The posterior distributions will be summarized to provide the posterior probability that the risk of DLT for each dose level of sabatolimab lies within the interval [50%, 100%] (i.e. excessive toxicity). After the first cohort, if this posterior probability is less than 25% for the two dose levels (400 mg and 800 mg), it would be recommended to start enrolling participants in Cohort 2 with sabatolimab 800 mg Q4W dose level.

Primary safety analysis in adolescent (Cohort 5 only) - Not assessable

The same Bayesian dose-DLT model will be used for the adolescent cohort (Cohort 5) if we have at least 3 participants evaluable in the DDS. The posterior probability that the risk of DLT for adolescents treated with sabatolimab at the dose recommended for adults lies within the interval [50%, 100%] (i.e. excessive toxicity) will be presented.

Primary efficacy analysis in adults (safety run-in and expansion parts)

A Bayesian design will be used to estimate the proportion of participants with no evidence of hematologic relapse after 6 cycles of study treatment in adults from the FAS treated with sabatolimab at the RDE in monotherapy and separately for adults treated with sabatolimab in combination with azacitidine, and to provide inferential summaries (e.g. mean, standard deviation, 95% credible intervals, and interval probabilities). This dual-criterion design will allow for base trial success not only on the statistical significance for superiority against the effect size expected with the Standard of Care (SoC) (the "null-value"), but also by considering a minimum clinically estimated effect size (the "decision value").

The decision criteria for trial success for adult participants treated with sabatolimab in monotherapy (participants enrolled in Cohorts 1, 2, 4 and treated at the RDE) are the following:

- 1. Statistical decision rule: the posterior probability that the proportion of adult participants who remain with no evidence of hematologic relapse after 6 cycles of study treatment is \geq 15% is at least 97.5% (statistical significance at 2.5% level, 1-sided).
- 2. Clinical decision rule: the posterior median for the proportion of adult participants who remain with no evidence of hematologic relapse after 6 cycles of study treatment is $\geq 30\%$.

The decision criteria for trial success for adults participants treated with sabatolimab in combination with azacitidine (participants enrolled in Cohort 3, "combination cohort") are the following:

- 3. Statistical decision rule: the posterior probability that the proportion of adult participants who remain with no evidence of hematologic relapse after 6 cycles of study treatment is \geq 30% is at least 97.5% (statistical significance at 2.5% level, 1-sided).
- 4. Clinical decision rule: the posterior median for the proportion of adult participants who remain with no evidence of hematologic relapse after 6 cycles of study treatment is $\geq 50\%$.

Inferential summaries (e.g. mean, median, standard deviation and 95% credible intervals) based on the Bayesian posterior distribution of the proportion of participants without a documented hematologic relapse will be presented by treatment arm (sabatolimab monotherapy and

Novartis	Confidential	Page 23 of 35
SAP – Amendment 1		CMBG453F12201

sabatolimab in combination with azacitidine). The results will also be presented with a frequentist formulation: the proportion of adult participants who remain with no evidence of hematologic relapse after 6 cycles of study treatment and the exact 95% confidence interval (Clopper and Pearson 1934), as well as the 1-sided p-value will be provided by treatment arm respectively (sabatolimab monotherapy and sabatolimab in combination with azacitidine). No adjustment of the type I error for multiplicity is planned for this study. The p-value will not be assessed due to the limited number of participants.

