5.1 Inclusion criteria

Participants eligible for inclusion in this study must meet all of the following criteria:

- 1. Signed informed consent must be obtained prior to participation in the study.
- 2. At the date of signing the informed consent form (ICF), eligible participants must be \geq 18 years for the adult cohorts; and \geq 12 years old but < 18 years old for the adolescent cohort (cohort 5), which will open after completion of Safety Run-in.
- Diagnosis of AML/secondary AML and received one prior aHSCT performed to control AML
 - Participants are eligible irrespective of response or MRD status at time of aHSCT
- 4. Participants in complete remission (< 5% bone marrow blasts, absence of circulating blasts, and absence of extramedullary disease) with MRD positivity by local assessment

- or by central assessment where required (e.g., USA sites), any time at \geq Day 60 after aHSCT.
- 5. Ability to provide a fresh bone marrow aspirate sample collected within 28 days from enrollment/randomization, and immediately shipped to a Novartis designated central laboratory for MRD testing.
- 6. Systemic GvHD prophylaxis or treatment [immunosuppressive treatment (IST)] completely tapered for at least two weeks prior to study entry. Prednisone dose ≤ 5 mg/day or equivalent corticosteroid dose is allowed.
- 7. Participants who are found with MRD positivity while still on or tapering systemic GvHD prophylaxis or treatment, MRD positivity must be re-confirmed at least 2 weeks after the last dose of IST
- 8. For the adult cohorts, participants must have an Eastern Cooperative Oncology Group (ECOG) performance status of 0, 1 or 2.
 - For the adolescent cohort, participants must have a Karnofsky (age \geq 16 years) or Lansky (age \leq 16 years) performance status score \geq 50%.
- 9. AST and ALT \leq 3 × upper limit of normal (ULN)
- 10. Total bilirubin $\leq 1.5 \times \text{ULN}$ (except in the setting of isolated Gilbert syndrome, in which case higher total bilirubin is allowed provided that conjugated bilirubin is $\leq 1.5 \times \text{ULN}$)
- 11. Estimated Glomerular Filtration Rate (eGFR) ≥ 30 mL/min/1.73 m² (calculated, based on local laboratory, using the Modification of Diet in Renal Disease (MDRD) formula in adults, and using the bedside Schwartz formula in the adolescent cohort).
- 12. ANC $\geq 1.0 \times 10^9 / L$
- 13. Platelet count $\geq 75 \times 10^9 / L$

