Date	Time point	Reason for update	Outcome for update	Section and title impacted (Current)	
10- June- 2021	FPFV	Creation of version 1.0	N/A - First version (based on protocol from 30-Sep-2020)	N/A	
03-Jul- 2024	Before primay CSR DBL	Creation of version 2.0	Amendment 2 (based on protocol from 24- March-2022) and MBG453 program termination	 Sections updated based on the protocol amendment 2 dated from 24 March 2022: Section 1.2.1: primary safety and efficacy estimand definitions Section 2.1: clarification of general definition Sections updated due to MBG453 program termination and thus, simplification of the analyses: Section 1: general statement added. Addition of a column in the 	
				 objectives tables to summarize the analyses performed for this final analysis. Section 2.1: general statement added. Section 2.3.1: simplification of protocol deviations summaries and deletion of pre-screened and screened failures analyses Section 2.4.1: cycle delays analysis deleted Section 2.4.2: Clarifications. Donor Lymphocyte Infusions will be only listed. Section 2.5 and 2.6: general statement added. Following endpoints were flagged as not assessable: Primary safety analysis in adolescents p-value deleted for the primary efficacy analysis in adults GvHD-free/relapse-free survival Section 2.7: AEs, SAEs, COVID-19 related events, GvHD, severe immune-related adverse events not attributed to GvHD, AESI and vital signs analyses simplified. Figures and corresponding tables for hematology parameters deleted Section 2.8: PK analyses simplified Section 2.6: Listings of all responses assessments added. 	

Date	Time point	Reason for update	Outcome for update	Section and title impacted (Current)
				Section 5: updated date of last exposure to study treatment and duration of exposure to study treatment derivation
				Typos corrected
				Clerical updates
				Updating of list of Abbreviatons

List of abbreviations

AE	Adverse event
AESI	Adverse events of special interest
aGvHD	Acute Graft-versus-Host disease
ALT	Alanine aminotransferase
AML	Acute myeloid leukemia
AST	Aspartate aminotransferase
ATC	Anatomical therapeutic classification
BLQ	Below the limit of quantitation
BMI	Body mass index
BP	Blood pressure
BSA	Body surface area
cGvHD	Chronic Graft-versus-Host disease
CI	Confidence interval
CR	Complete remission
CRi	Complete remission with incomplete hematologic recovery
CSR	Clinical study report
СТС	Common toxicity criteria
CTCAE	Common terminology criteria for adverse events

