Due to the study recruitment halt and the termination of the MBG453 program for non-safetyrelated reasons, this study will be terminated early. Thus, not all protocol planned derivations and analyses will be performed. Although described in this document, please refer to table of endpoints for the selected planned analyses of this final CSR. Any secondary endpoint analyses not conducted due to limited number of patients available, will be documented as such in the final CSR and indicated as zero patients with an explanation for mandatory results posting, if required.

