Study treatment consists of cycles of sabatolimab (400 mg or 800 mg) administered intravenous on Day 1 of each 28-day cycle for the monotherapy cohorts (Cohorts 1, 2, 4 and 5). Study treatment consists of cycles of sabatolimab (400 mg or 800 mg) administered on Day 5 of each 28-day cycle in combination with azacitidine administered intravenous or subcutaneous at 50 mg/m² daily during the first 5 days of each cycle (Cohort 3). Crossover between the different sabatolimab doses (400 mg and 800 mg Q4W) is not permitted at any time during the study. Study treatment may continue for up to a maximum of 24 cycles or until the participant experiences a documented hematologic relapse from CR/CRi (as defined by ELN 2017 Döhner et al 2017) or unacceptable toxicity, whichever is earlier.

Interim analyses are planned for the monitoring of safety data, and will be conducted after each dose level cohort of the safety run-in part to determine the RDE. The first safety review meeting to assess whether sabatolimab 400 mg Q4W is not meeting overdose criteria (i.e. an excessive incidence of Dose Limiting Toxicities (DLT)) will take place after at least 6 evaluable participants treated with sabatolimab 400 mg Q4W have completed 2 cycles of treatment (Cohort 1). If no safety concerned are observed at this dose level, a second safety review meeting to assess whether sabatolimab 800 mg Q4W is not meeting overdose criteria will take place after at least 9 evaluable participants treated with sabatolimab 800 mg Q4W is not meeting overdose criteria will take place after at least 9 evaluable participants treated with sabatolimab 800 mg Q4W have completed 2 cycles of treatment (Cohort 2). Details on the definition of dose limiting toxicities (DLT) are presented in study protocol Table 6-2.

The efficacy of sabatolimab when given as a single agent or in combination with azacitidine will be assessed after all adults from Cohorts 3 and 4 have completed 6 cycles of treatment (primary efficacy objective). The end of study is defined as all participants having completed the safety and post-treatment follow up (if applicable), or having died, been lost to follow-up or having withdrawn consent to further participation in the study.

Due to the study recruitment halt and the termination of the sabatolimab program for non-safetyrelated reasons, the study will be terminated early. Based on the limited numbers of participants, the final CSR will be written with a limited number of analyses.

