- 3. Treatment of interest: Treatment with sabatolimab or sabatolimab in combination with azacitidine taken for the entire study duration post aHSCT. One estimand for each of the two treatments of interest (sabatolimab in monotherapy and sabatolimab in combination with azacitidine) will be considered.
- 4. Handling of intercurrent events:

- Failure to complete 6 cycles of treatment due to death for any reason or relapse: a participant who dies or has a relapse before completing 6 cycles of treatment will be considered as a non-responder (composite variable strategy).
- Start of donor lymphocyte infusions (DLI) or a new anti-neoplastic therapy before completing 6 cycles of study treatment: a participant who starts a DLI or a new antineoplastic therapy before completing 6 cycles of treatment will be considered as a non-responder (composite variable strategy).
- Failure to complete 6 cycles of treatment due to reasons other than relapse and death for any reason (including due to adverse events, graft vs. host disease for example): all participants with an adequate response assessment (other than "unknown" response) will be taken into account regardless of any study treatment interruption or permanent discontinuation; for a participant who stops the study due to reasons other than relapse or death, we will ask the participant to perform a response assessment 6 months after starting study treatment; a participant with no evidence of hematologic relapse 6 months after starting treatment will be considered a responder (treatment policy strategy).
- 5. Summary measure for the primary efficacy estimand is the proportion of participants with no evidence of hematologic relapse with its exact 95% confidence interval for each of the two study treatment of interest: sabatolimab in monotherapy and sabatolimab in combination with azacitidine. The trial will be successful if at least one of the treatments of interest (sabatolimab monotherapy or sabatolimab in combination with azacitidine) meets both statistical and clinical significance.

The **primary safety estimand for adolescent participants** included in this study is described by the following attributes:

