- Population: Adolescent participants with AML who are in CR after aHSCT and at high risk of relapse defined as positive MRD any time at ≥ Day 60 after aHSCT (with a confirmed MRD positivity at least 2 weeks after systemic immunosuppression has been tapered off) and who are exposed to study treatment for at least 2 cycles or who experienced a DLT within the DLT observation period.
- 2. Primary variable: Proportion of adolescent participants who experience at least one DLT including but not limited to aGvHD and cGvHD as per investigator assessment between Cycle 1 Day 1 (first administration of MBG453) and end of Cycle 2 (Day 28).
- 3. Treatment of interest: Treatment with sabatolimab as monotherapy at the recommended dose for adults taken for the entire study duration post aHSCT.
- 4. Handling of remaining intercurrent events:
 - Delay to start Cycle 3 due to any reason: a DLT that will occur after Day 28 of Cycle 2 and before starting Cycle 3 will be considered in the analysis (treatment policy strategy).
 - Failure to start Cycle 3 due to any reason: a DLT that will occur up to the theoretical last day of Cycle 2 (Cycle 2 Day 28) will be considered in the analysis regardless of permanent discontinuation after the dose of sabatolimab in Cycle 2 (treatment policy strategy).

Novartis	Confidential	Page 15 of 35
SAP – Amendment 1		CMBG453F12201

5. Summary measure for the primary safety estimand is the proportion of participants with treatment-emergent dose limiting toxicity as per investigator assessment reported in the first 2 cycles.

As Novartis decided to permanently hold recruitment on December 20th 2023 for non-safetyrelated reasons, the study enrolled only one adolescent in part 2. Thus, all analyses on the adolescent cohort could not be performed and only listings will be provided. Therefore this objective could not be evaluated.

2 Statistical methods

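### SAP v2 drops the p-value for small numbers but keeps a success rule labelled as significance at the one-sided 2.5% level, which the rule does not deliver at many sample sizes below plan

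*SAP*

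**What the plan says.** SAP 2.5.2 declares success on two criteria per treatment. For monotherapy, the posterior probability that the relapse-free proportion is 15% or more "is at least 97.5% (statistical significance at 2.5% level, 1-sided"), and the posterior median must reach 30%. The combination rule has the same form and the same label, with 30% and 50%. SAP 1.2.1 keeps the overall claim: "The trial will be successful if at least one of the treatments of interest (sabatolimab monotherapy or sabatolimab in combination with azacitidine) meets both statistical" (the sentence then names the clinical criterion as well).

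SAP v2 was written after the halt and responds to it in part. The change log records "p-value deleted for the primary efficacy analysis in adults", and SAP 2.5.2 gives the reason: "The p-value will not be assessed due to the limited number of participants". SAP 1.1 adds: "Based on the limited numbers of participants, the final CSR will be written with a limited number of analyses". The SAP introduction warns that some described analyses will not be done and says "please refer to table of endpoints for the selected planned analyses of this final CSR". That table (Table 1-1) marks primary efficacy Yes and does not say whether the success rule is still applied.

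SAP section 3 gives cutoffs only for 25 and 20 participants. SAP section 4 lists no changes to protocol-specified analyses. The SAP names no prior for the efficacy analysis; Protocol 12.8.1 gives Beta(1,1), but only for the sample size calculations.

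**The concern.** The label is a frequentist statement: it says how often the rule would declare success if the true proportion were the null value. A fixed 97.5% posterior threshold does not have that property at every n. The cutoff is a whole number. While it stays fixed the false-positive rate rises with n, and when it steps up the rate drops, so the rate is a sawtooth. Protocol 12.8.1 checked it only at n=25 and n=20, and recruitment stopped early.

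At some sizes the final report could therefore announce 2.5% significance and trial success beside an exact 95% interval, also required by SAP 2.5.2, that clearly includes the null. The p-value, which would show the mismatch most directly, has been removed.

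**Working it through.** **Inputs.** Null values 15% and 30%, posterior threshold 97.5%, median thresholds 30% and 50% (SAP 2.5.2; Protocol 12.4.2). Prior Beta(1,1) (Protocol 12.8.1), assumed to carry over to the analysis.

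**Method.** After x of n without relapse the posterior is Beta(1+x, 1+n−x). The cutoff c is the smallest x with P(p ≥ p0 | x, n) ≥ 0.975 and posterior median at or above the threshold. The exact false-positive rate is P(X ≥ c) for X ~ Binomial(n, p0).

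**Planned sizes.**
- Monotherapy, n=25: 7/25 gives posterior probability 0.968 and fails; 8/25 gives 0.989 with median 32.9% and passes. P(X ≥ 8 | 25, 0.15) = 0.0255 (protocol: 2.5%). Power is 69.4% at a true 35% and 84.6% at 40%, as stated.
- Combination, n=20: 10/20 gives 0.974 and fails; 11/20 gives 0.991 with median 54.7% and passes. P(X ≥ 11 | 20, 0.30) = 0.0171 (protocol: 1.7%). Power at 60% is 75.5%, as stated.

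**Range of n.** The achieved adult numbers are not given. SAP 1.2.1 says "the study enrolled only one adolescent in part 2", and Protocol 5.1 says of the adolescent cohort "which will open after completion of Safety Run-in". I therefore assume the run-in reached its minimum evaluable numbers: at least 6 adults at 400 mg, or 9 at 800 mg, whichever is the expansion dose. No such floor can be inferred for the combination; n=6 to 19 is shown first, then smaller sizes.

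**Monotherapy, p0 = 15%**

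| Cutoff/n | Rate | Cutoff/n | Rate |
|---|---|---|---|
| 3/6 | 4.73% | 6/16 | 2.35% |
| 3/7 | 7.38% | 6/17 | 3.19% |
| 4/8 | 2.14% | 6/18 | 4.19% |
| 4/9 | 3.39% | 6/19 | 5.37% |
| 4/10 | 5.00% | 7/20 | 2.19% |
| 4/11 | 6.94% | 7/21 | 2.87% |
| 5/12 | 2.39% | 7/22 | 3.68% |
| 5/13 | 3.42% | 7/23 | 4.63% |
| 5/14 | 4.67% | 8/24 | 1.99% |
| 5/15 | 6.17% | | |

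Five of 19 sizes are within 2.5% (n=8, 12, 16, 20, 24) and 13 are at 3.0% or more. From n=9 (800 mg) the range is 2.0% to 6.9%, with 11 of 16 at 3.0% or more.

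**Combination, p0 = 30%**

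| Cutoff/n | Rate | Cutoff/n | Rate |
|---|---|---|---|
| 5/6 | 1.09% | 8/13 | 1.82% |
| 5/7 | 2.88% | 8/14 | 3.15% |
| 6/8 | 1.13% | 9/15 | 1.52% |
| 6/9 | 2.53% | 9/16 | 2.57% |
| 6/10 | 4.73% | 9/17 | 4.03% |
| 7/11 | 2.16% | 10/18 | 2.10% |
| 7/12 | 3.86% | 10/19 | 3.26% |

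Five of 14 are at 3.0% or more (n=10, 12, 14, 17, 19). At n=3 to 5 the rates are 2.70%, 0.81% and 3.08%; with 1 or 2 participants the rule cannot be met.

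The posterior-median criterion never raises the cutoff at these sizes, so the clinical rule does not protect the error rate.

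**Rule against the exact 95% interval**
- 4/11 monotherapy: posterior probability 0.976, median 37.9%, rule met; interval 10.9% to 69.2% includes 15%.
- 6/10 combination: posterior probability 0.978, median 58.8%, rule met; interval 26.2% to 87.8% includes 30%.
- 8/25 (planned): interval 14.95% to 53.5%, only just including 15%.
- 11/20 (planned): interval 31.5% to 76.9%, excludes 30%.

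**Other prior.** With Beta(0.5, 0.5), monotherapy n=6 to 24 gives 1.2% to 5.0%, with 8 of 19 at 3.0% or more. The rate falls to 1.2% at n=7, 1.6% at n=11 and 1.7% at n=15, but stays at 5.0% at n=10. Combination cutoffs for n=3 to 19 do not change.

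**The case against.** The best reply is that the success wording is left over. SAP v2 keeps much superseded text and overrides it with general statements; the p-value sentence itself is kept and then withdrawn. But where v2 drops something it says so: adolescent safety and GvHD-free/relapse-free survival are flagged as not assessable and the p-value is withdrawn by name. The success rule has no such flag and its endpoint is selected. Its status is at best unclear.

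Second, the operative criterion, a 97.5% posterior probability, means the same at any n; only the parenthesis depends on size. That is correct, and it is why the parenthesis is what needs changing. It was already slightly approximate at n=25.

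Third, the largest figures are worst cases. The 7.4% needs n=7, hence a 400 mg expansion dose with almost no expansion enrolment, although 800 mg is preferred. At 8 or 12 the label holds. Several monotherapy examples also vanish under Beta(0.5, 0.5). All this stands. However, Beta(1,1) is the only prior in the documents, 5.0% at n=10 survives the change, and the combination rates are unaffected.

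Fourth, the programme has ended, nothing in the documents makes a later decision depend on the success claim, and readers will see the interval. This limits the consequence but does not make the label correct.

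**Conclusion.** The concern holds. SAP v2 attaches a 2.5% error rate to a rule that, under Beta(1,1), has exact rates of 2.0% to 7.4% for monotherapy (n=6 to 24) and 1.1% to 4.7% for the combination (n=6 to 19). It does so in the same section that gives up the p-value for lack of numbers. The arithmetic is exact. What is uncertain is where the trial landed: I assume final numbers below plan, the Beta(1,1) prior, and a run-in that reached its minimum evaluable size. No actual inflation is claimed, since at several sizes the label would be true. The defect is that its truth depends on an n to which the SAP never ties it. It should be corrected because it concerns the headline success claim; the estimates and intervals are unaffected.

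**What to change.** Preferred, and consistent with dropping the p-value: state in SAP 1.2.1 and 2.5.2 that the dual-criterion success rule will not be formally evaluated, and report the proportion, the posterior summary and the exact 95% interval for each treatment.

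If the rule is kept, delete the parenthetical significance label from both statistical criteria, state that the Beta(1,1) prior applies to the analysis, and report the cutoff and exact type I error at the realised n for each treatment.

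The cost is SAP wording only. Under the preferred option the sponsor gives up a formal success claim from the truncated data.
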